### 5.4.2 Mystery Shoppers

Two mystery shoppers will visit each location separately. Each HIV/STI/PrEP clinic will require two round-trip visits during the mystery shopper phase. There are up to 60 registered HIV testing sites offering free HIV tests for men within each city's 25-mile radius: Atlanta (up to 20 sites), Houston (up to 26 sites), and Philadelphia (up to 55 sites). We will use time space sampling to ensure that varying days (weekdays versus weekends when applicable) and times (e.g., morning versus afternoon or evening) are selected for visits, thereby maximizing the chance of getting different counselors at each agency. The project manager will create a calendar for mystery shoppers to know when and where they will be getting tested. We will reimburse the mystery shoppers for all charges linked to their testing experiences. Mystery shoppers will be instructed to be honest about their sexual behaviors during their visits. By avoiding creating 'personas' or 'scripts,' shoppers will increase the social validity of the assessment and avoid arousing suspicion due to exaggerated or unrealistic scenarios. Upon completion of a testing visit, the mystery shoppers will complete the Qualtrics site follow-up survey immediately. Mystery shoppers will also be asked to summarize their qualitative impressions using an open text field.

### 5.4.3 Assessment of sites' satisfaction with biannual performance reports

Directors of ten randomly-selected agencies in each city will participate in a one-time 60-90 minute semi-structured interview that will focus on 4 domains: (1) existing prevention services used and/or promoted by the agency, (2) agency (internal) resources currently missing, that if identified and addressed, could improve delivery of HIV/STI and PrEP services to YMSM, (3) feedback on the biannual evaluation assessments and their use for service-delivery improvements, and (4) the advantages and disadvantages of GC rollout within ASOs. We will interview providers via video conference in a private office at the University of Pennsylvania to maximize candidness and privacy while decreasing travel-related costs. We will use BlueJeans, a simple and low cost alternative that requires no server infrastructure to set up or maintain and

allows providers to be HIPAA-compliant. The iTech Technology Core will facilitate access to and provide any technical support needed.

#### 5.4.4 Mystery Shopper Training:

We will work with the ATN site in each city to recruit and enroll HIV-negative YMSM (ages 18-24) who are interested in serving as mystery shoppers. We plan to recruit and enroll a diverse group of 10-15 mystery shoppers per city.

Shoppers will be trained to work with our site assessment tool to optimize standardized data collection across sites. A key aspect of the training will be role-playing through mock clinical scenarios. They will also receive training to strengthen their self-efficacy to feel empowered as a client. Specifically, we will conduct role-plays with different scenarios and interactions that might occur during a visit. We will underscore the importance of being well versed in their rights and procedures, and provide skills on how to respond to worst-case scenarios (e.g., how to turn down any unwanted procedures) were they ever to occur.

#### 5.4.5 Intervention Monitoring/Quality Control

The RCT will be managed through weekly site meetings, monthly meetings with iTech Core Leaders, and annual meetings. Research staff will meet regularly to ensure standardization of procedures, and share details on recruitment strategies. Standardization of RCT activities will be ensured by providing consistent training to all study staff and by using a central research protocol that will be developed for the project to ensure guidelines are followed.

## 6.0 EVALUATIONS AND MEASURES

### 6.1 Behavioral Evaluations

#### 6.1.1 Pre-intervention (Baseline) Evaluations/Measures

- *Socio-demographic information:* We will include questions on race/ethnicity, educational attainment, employment status, housing status, and history of incarceration, sexual identity, and “outness” to their social network.
- *HIV Testing:* The baseline survey will include questions on HIV testing history.
- *STI Testing:* At baseline, we will assess STI testing history and knowledge about STIs. We will ask participants what STIs they have been tested for, the date of their most recent STI test (if known), and whether a medical provider has ever diagnosed them with an STI.
- *Mechanisms of Change:* We will assess YMSM’s psychosocial correlates predicted to adopt HIV services (i.e., Attitudes, Norms, Self-Efficacy, and Behavioral Intentions to get HIV tested). Integrated Behavioral Model constructs will be assessed with 3 subscales assessing YMSM’s attitudes, social norms, and behavioral intentions that we have used in the past with this population. Each attitude item is measured with three five-

point semantic differential scales (good-bad; worthless-valuable; pleasant-unpleasant). Social norms assess the extent to which participants felt that friends and family believed he should test for HIV on a 1 to 5 scale. Behavioral intentions items assess participants' intention to adopt HIV testing, on a 1 (very unlikely) to 5 (very likely) scale. Self-efficacy to access HIV/STI services and to discuss sexuality-related issues with provider will be ascertained, as well as YMSM's perceived confidence of visiting a testing site or requesting a home kit.

- Sexual Risk Behavior:* Sexual risk behavior will be assessed using the Sexual Practices Assessment Schedule used in previous online studies with YMSM to explore the number of occasions of different sexual acts (oral, anal; receptive, insertive) with three different types of partners (romantic interest, casual partner “hookup,” or friend with benefits), use of condoms during the past 3 months, and knowledge about partners' HIV status and PrEP use. Assessments ascertain sexual behaviors with male and female partners, and will be asked at each follow-up. At-risk sex will be defined as any anal intercourse without condoms and/or PrEP that occurs with a person of known positive or unknown sero-status. We will assess the number of partners with whom participants had “at-risk sex.”
- PrEP Awareness and Willingness:* The survey will contain a brief description of PrEP to orient the participant. Questions are adapted from recent studies of PrEP attitudes with YMSM. PrEP awareness will be a single item measure of whether the participant has heard of PrEP (yes/no/I don't know). PrEP willingness will be measured with an existing 8-item scale developed for YMSM to gauge likelihood of PrEP use across different conditions (e.g., partner types; experiencing potential side effects).
- Technology and Social Media Use:* Given the online interface of the intervention, we will include Pew Internet Survey questions regarding use of different devices, the number of hours spent online through each device, the reasons for social media use, sites commonly frequented, and extent to which the Internet supplements face-to-face interactions. We will also measure AMSM's frequency of use of social media to look for HIV or sexual health-related information, and their online partner-seeking behaviors
- ATOD (alcohol, tobacco, and other drug) use:* We will assess frequency of ATOD use (as measured in NSDUH) over the past 30 days (3 months in 3-, 6-, 9-, and 12-month follow-up surveys) for alcohol, tobacco products, cannabis, cocaine, amphetamine type stimulants, inhalants, sedatives or sleeping pills, hallucinogens, and opioids. We will also ask age of onset. If respondents indicate alcohol use, we will ask the Alcohol Use Disorders Identification Test (AUDIT) developed by the WHO (World Health Organization). AUDIT is a 10-item screening questionnaire with 3 questions on the amount and frequency of drinking, 3 questions on alcohol dependence, and 4 on problems caused by alcohol.
- Psychological Distress:* We will measure this using existing, well-validated scales. We will use subscales from the Brief Symptom Inventory to measure depressive symptoms and anxiety symptoms. Depressive symptoms include 6 items rated on a 5-point scale (1=never, 5=very often). Items include feelings of loneliness, blue or sad, and having

thoughts of ending one's life. Anxiety also includes 6 items measured on the same 5-point scale and includes reporting nervousness or shakiness, feeling fearful, or suddenly scared for no reason. We will use the 10-item Rosenberg Self-Esteem^66, measured on 4-points (0=Strongly disagree-3=Strongly agree).

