### 3.0 STUDY DESIGN

#### 3.1 Study Phases

In this four-year study, we will enroll 480 self-reported HIV-negative or sero-status unaware, sexually active YMSM (ages 15-24) across three sites and randomize them into the GC intervention condition or to an attention-control condition. Primary outcomes will include (1) use of HIV prevention services (HIV testing, STI testing) and PrEP awareness and willingness. As secondary outcomes, we will assess PrEP use, sexual risk behaviors, and the linkage and retention in care among newly diagnosed HIV+ cases. We will also examine changes in GC's theorized mechanisms of change, including YMSM's attitudes, norms, self-efficacy, and behavioral intentions to adopt HIV prevention services.

Control condition: Participants randomized to the control condition will have access to the site locator portion of the Get Connected website, which includes information on HIV prevention services. While the provision of a test locator is a form (albeit weak) of an intervention, we felt that withholding referrals to testing and care services would be unethical given YMSM's vulnerability to HIV and STIs. Furthermore, given the availability of search engines to locate HIV/STI testing sites, the test locator condition may be considered usual care. Nevertheless, by providing the testing site locator only, we will be able to test the effect of the GC intervention condition (i.e., user-tailored content focused on HIV/STI testing and PrEP referral and the linkage to high-quality agencies) against the usual care control condition.

Intervention condition: Using a consensus approach to conceptualize health behavior change, the model guiding GC synthesizes The Integrated Behavioral Model and Self-Determination Theory as the theoretical underpinnings of our intervention. These theories emphasize social cognitive factors that impact behavior change and have informed HIV interventions. Consistent with these theories, GC content follows motivational interviewing (MI) principles by focusing on resolving ambivalence about HIV prevention behaviors, increasing self-efficacy for change, and enhancing motivation moving toward action. The intervention was developed by customizing content based on YMSM's psychosocial and sexual

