## 5.4 Intervention/Investigation Procedures

### 5.4.1 Get Connected Intervention

Participants will complete a 30- to 45-minute baseline survey that includes questions on lifetime HIV testing history, lifetime STI testing history and knowledge about STIs, date of their most recent STI test (if known), and whether they were ever diagnosed with an STI. GC will use baseline survey data to select and deliver personalized, tailored content to YMSM assigned to the intervention. Furthermore, as part of the participant's baseline visit, study staff will collect contact information where participants may be reached for follow-up assessments. We will use best practices to retain participants (e.g., collecting participant's cell phone number, email address, Facebook, WhatsApp, and/or Skype username, and contact information for 2 peers who could help us contact them). Additional surveys will occur at 1, 3, 6, 9, and 12 months after intervention initiation, and can be completed online. These follow-up surveys will repeat many of the questions from the baseline survey and will also include additional questions on HIV and STI testing in each 3-month period, including test results. These surveys will be the same for participants in the control and intervention arms. For participants in the intervention arm, the GC WebApp will be retailored after each follow-up survey, based on any different information provided on key questions.

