### 6.1.2 On-study Evaluations/Measures

- *HIV Testing:* Follow-up surveys will repeat the HIV testing questions in each follow-up survey. The HIV testing outcome will be: the proportion of MSM tested for HIV two or more times at least 3 months apart in the 12-month follow-up period (“frequent tester”). As an additional analysis, we will also examine the proportions of participants who receive one HIV test.
  - Among self-reported newly diagnosed HIV+ cases, we will measure their linkage and engagement with appropriate medical care after initial diagnosis using criteria employed in prior ATN protocols with youth. We will define linkage as an HIV-related medical visit within 45 days of referral, and engagement as a second HIV-related medical visit within 16 weeks of initial visit. Onset of ART initiation, self-reported adherence to ART, and viral suppression are exploratory indicators, as we recognize that our follow-up period may not be a sufficient amount of time to see these changes.
- *STI Testing:* The STI testing outcome is defined as the proportion of YMSM tested for STIs at least once in the 12-month follow-up period. We will ask participants what STIs they have been tested for, the anatomic sites where they were tested, the date of their most recent STI test (if known), and whether a medical provider had diagnosed them with an STI. In the follow-up surveys, we will ask participants whether they had been tested for STIs in the past 3 months (for the 1-month follow-up survey, we ask about the past 30 days). If STI testing is reported, we will ask participants to indicate what tests they received, and whether they were diagnosed with an STI by a medical provider.
- *PrEP Use:* At each follow-up assessment, PrEP-eligible HIV-negative YMSM (per CDC guidelines) will be asked whether they have begun using PrEP. We will also ascertain if a provider recommended PrEP and/or were offered a prescription for PrEP.
 

*Site Evaluations:* Across both trial arms, YMSM who report testing in the prior 3 months will complete self-evaluation forms of their testing experiences to assess comfort, quality, and concerns after visiting a site for HIV/STI testing and PrEP prevention services. The assessment form is the same form used by the mystery shoppers. We will use these data to update the WebApp and to send aggregate data of YMSM's satisfaction with services to agencies biannually.

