### 7.3.3 CASI Data

Data collected using a web-based CASI method will be on a portable computer, tablet, or mobile phone via an internet-based application. All survey data will be collected using SurveyGizmo. Data will remain confidential; no personal identifying information will be collected during the computer session. The participant's unique SID# will be used in order to link the interview responses to the participant's CRF data.

Self-administered surveys will be done at baseline and months 1, 3, 6, 9, and 12. They will be completed by participants on personal devices or laptop or desktop computers via surveys hosted on SurveyGizmo.com. We use SSL encryption for transfers of information online and data will be stored in the secure, HIPAA-compliant servers of SurveyGizmo. The Emory AC team maintains a business partner HIPAA agreement with SurveyGizmo.

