## 10.3 Statistical Analysis Plan

10.3.1 We will use the general framework of generalized linear mixed models (GLMM) to test for intervention effects over time. Note that some of our outcomes are binary, some count and some continuous traits, and thus need to be treated differently. The general form of the GLMM will be  $g(\mu_{ij}) = \beta_0 i + \beta_{cov} Covariates_{ij} + \beta_{Time} j + \beta_{Trt} Trt_{Armi} + \beta_{Arm \times Time}$ , where  $\beta$  is the mean response corresponding to subject  $i$  at Time  $j$  (baseline and 4 follow-ups), with its appropriate link function (identity for continuous outcome, logit for binary outcome and natural log for count outcomes);  $Trt = 1$  if the  $i$ -th subject is in the intervention group and 0 if the  $i$ -th subject is in the attention-control group. The interaction coefficients are of interest here, measuring the difference in the rate of change in outcome across the two treatment groups over time. The subject-specific random intercepts are assumed to be normally distributed with a common variance and they account for within-person correlation. We will also explore if we need a subject-specific random-slope corresponding to visit in the above model. Maximum likelihood estimation will be used for fixed effect parameters. Models will be compared according to information criterion like AIC, BIC. For some binary outcomes like HIV testing, we will perform an aggregate analysis after collapsing across the repeated measures using simple logistic regression comparing whether the probability of having tested at least once over the entire FU period is different across treatment groups, after adjusting for baseline values. To ensure robustness, we will also apply an exchangeable working correlation structure to its corresponding generalized estimating equation (GEE) model. We will also conduct exploratory regression analyses to examine city differences in the outcomes. These regressions will be run with group assignment and city in the model, controlling for socio-demographic characteristics.

Interactions between group assignment and city will be tested to explore potential site-specific moderators of treatment effect.

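### As written, the month-1 sexual risk items look back 3 months, so one third to two thirds of that window precedes randomisation and the month-1 contrast is diluted

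*Combined protocol and SAP*

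**What the plan says.** Section 3.1 makes sexual risk behaviour a secondary outcome: "As secondary outcomes, we will assess PrEP use, sexual risk behaviors, and the linkage and retention in care". Section 6.1.1 describes the measure as occasions of different sexual acts by partner type, "use of condoms during the past 3 months", and a derived number of partners with whom at-risk sex occurred. It then extends the measure beyond baseline: "Assessments ascertain sexual behaviors with male and female partners, and will be asked at each follow-up". Section 5.4.1 adds: "These follow-up surveys will repeat many of the questions from the baseline survey". No separate recall is given for month 1.

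Two neighbouring measures do have one. Alcohol, tobacco and other drug use is asked "over the past 30 days (3 months in 3-, 6-, 9-, and 12-month follow-up surveys", so month 1 keeps the 30-day window. For STI testing, section 6.1.2 says "for the 1-month follow-up survey, we ask about the past 30 days".

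The schedule is "Self-administered surveys will be done at baseline and months 1, 3, 6, 9, and 12" (section 7.3.3). Consent, randomisation and the baseline survey take place at one visit (section 5.1). The month-1 survey is emailed 30 days after baseline (section 8.1) and is paid for if completed within 30 days of that email (section 8.2).

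On analysis, section 10.1 applies its regressions to the secondary outcomes too. Section 10.3 sets out a longitudinal mixed model for binary, count and continuous outcomes and says: "The interaction coefficients are of interest here, measuring the difference in the rate of change in outcome across the two treatment groups over time".

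**The concern.** Behaviour before randomisation cannot differ between arms because of the intervention. If the month-1 window is mostly pre-randomisation, the month-1 contrast mixes a null period with an exposed one and is pulled towards no effect. Those same days were also reported at baseline. From month 3, on the email schedule, a 3-month window is wholly post-randomisation. The share of exposed time therefore changes once, between months 1 and 3, and an immediate, constant effect can look as if it arrived late.

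Month 1 matters here because the pilot trial summarised in section 1.2.3 reported a reduction in number of sexual partners (effect size 0.21) at its 30-day follow-up. An early effect is therefore plausible on the sponsor's own evidence, and this is the wave in which most of it could be hidden. The month-1 adjustments for STI testing and substance use make the missing one stand out.

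**Working it through.** The documents give no figure for the recall overlap and no power calculation for sexual risk behaviour, so there is no stated result to reproduce.

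**Inputs from the plan**
- Recall: 3 months, taken as 90 days (section 6.1.1).
- Time zero: the baseline visit, which includes randomisation (section 5.1).
- Month-1 completion: from day 30 (email, section 8.1) to day 60 (last paid day, 30 + 30, section 8.2).
- Five follow-ups: months 1, 3, 6, 9 and 12 (section 7.3.3).

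**Assumed, not in the plan:** a rate ratio of 0.80 acting from day 0 and constant thereafter, and counts proportional to time.

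**Step 1. Share of the window before randomisation** = (90 − t)/90, where t is the completion day.
- Day 30: 60/90 = 67%.
- Day 45: 45/90 = 50%.
- Day 60: 30/90 = 33%.

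A 91-day window gives 67%, 51% and 34%. At month 3, completed on the email schedule, the share is about 0%.

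**Step 2. Rate ratio seen at month 1** = (1 − f) × 1 + f × 0.80, where f is the share after randomisation.
- Day 30, f = 1/3: 0.667 + 0.267 = 0.933. Share of the log effect: ln 0.933 / ln 0.80 = 0.31.
- Day 60, f = 2/3: 0.333 + 0.533 = 0.867. Share of the log effect: ln 0.867 / ln 0.80 = 0.64.

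**Step 3. Equal-weight average over five follow-ups**, months 3 to 12 showing the full effect.
- Day 30: (0.31 + 4)/5 = 0.86 of the log effect, a 14% loss; average rate ratio about 0.825.
- Day 60: (0.64 + 4)/5 = 0.93 of the log effect, a 7% loss.

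**Step 4. Apparent step from month 1 to month 3** (ratio of rate ratios): 0.80/0.933 = 0.86 at day 30 and 0.80/0.867 = 0.92 at day 60. After month 3 the effect is flat.

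**Step 5. Illustrative simulation.** Poisson GEE on the five follow-ups, without baseline, 200 per arm, 400 trials per scenario, month 1 answered at day 30. Assumed: control mean of 3 events per 3 months, gamma heterogeneity with shape 1, independence working correlation with robust standard errors. The table shows how often the arm-by-time test rejects.

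| Constant rate ratio | 3-month recall at month 1 | 30-day recall at month 1 |
|---|---|---|
| 1.0 | 6% | 6.5% |
| 0.80 | 44% | 7.5% |
| 0.70 | 87% | 6% |
| 0.60 | 99.8% | 6.5% |

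With no effect, the 3-month recall creates none. With a constant effect, it produces a change over follow-up that is not there. These rates apply to a model of this form only.

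**The case against.** **The month-1 recall is inferred.** The 3-month phrase occurs in the baseline section and attaches most directly to condom use. The sentence extending the items to follow-up gives no recall, section 5.4.1 says many rather than all questions are repeated, and the questionnaire is not in the documents. A reader might infer that a 3-month window at month 1 is established fact, but the documents support only that this is what the text says as written. The objection stands as a limit on certainty. It does not remove the need to state the recall.

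**The analysis link is looser than it looks.** A reader might infer that section 10.1 carries the arm-by-time test over to secondary outcomes. What it repeats are regressions on group assignment, then with covariates and group-by-characteristic interactions. The section 10.3 model may well be used for these counts, but its time index includes baseline. An immediate, constant effect is then itself an arm-by-time interaction, so a significant result there is not an artefact of recall. The simulated rejection rates do not carry over to that model; they fit a follow-up-only model such as those in section 2.4, which are written for binary and continuous outcomes. This stands. The month-1 contrast is still diluted under either model.

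**Section 10.3 counts four follow-ups where five are scheduled.** If month 1 were the one omitted, that model would avoid the problem. Nothing says so, and section 2.4 plans for five.

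**Size.** Two thirds is the day-30 value and falls to one third by day 60. A reader might infer an effect that keeps growing; the arithmetic gives one step, then a flat line.

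**Remedy.** Distinct partners do not accumulate in proportion to time, so neither the dilution formula nor a log-days offset fits them well. This stands and shapes the fix.

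**Conclusion.** The point holds in limited form. As written, one third to two thirds of the month-1 window for sexual risk behaviour precedes randomisation, and no month-1 exception is stated. For an assumed constant rate ratio of 0.80, month 1 would show 0.87 to 0.93, and 7% to 14% of the log effect would be lost in an equal-weight average over five follow-ups. A constant effect can also appear to step up once, between months 1 and 3.

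This rests on the text being what is fielded, on an effect starting at day 0, and on counts proportional to time, which suits acts better than partners. The bias is towards no effect in one wave of a secondary outcome. The documents do not support reading it as a source of false positives or as a threat to the HIV testing outcome or the sample size.

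**What to change.** State the month-1 recall for the sexual behaviour items. Ask them for the period since the baseline visit, or for the past 30 days as for STI testing and substance use. Asking since the baseline visit copes better with late completers.

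Add to the analysis plan:
- For act counts, use a log(recall days) offset so that month 1 is comparable with the 3-month waves.
- For counts of distinct at-risk partners, do not use the offset. Leave month 1 out of the between-arm and arm-by-time tests and use months 3 to 12.
- If the survey cannot be changed, leave month 1 out in the same way for all sexual risk outcomes.

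The cost is a wording change in one survey and a short addition to the analysis plan. Month-1 counts become sparser and less comparable with the 3-month baseline, or one wave is lost. A 3-month look-back at month 3 will still cover days already reported at month 1. Those days are post-randomisation, so they do not dilute the contrast.

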## **10.0 STATISTICAL/ANALYTIC CONSIDERATIONS**

### **10.1 Introduction**

10.1.1 We will test the efficacy of GC in increasing HIV-negative or HIV-unknown YMSM's successful uptake of HIV and STI testing (e.g., routine HIV/STI testing) and increase in PrEP awareness and willingness, as compared to the attention-control condition over a 12-month period. Descriptive statistics of the psychosocial and demographic characteristics of the participants will be described for all and by intervention group. These will be compared between treatment groups using t-tests or Wilcoxon rank sum tests for continuous variables and chi-square tests for categorical variables. To test for intervention efficacy, we will conduct primary

analyses of our primary outcomes using regression analyses to compare our treatment group to the control using the appropriate link function (identity for continuous outcome, logit for binary outcome, and natural log for count outcomes). The regression will be run with group assignment only in the model, as well as, controlling for participants' socio-demographic characteristics, ATOD and psychological distress, and intervention-related process data (e.g., frequency of use, acceptability). Interactions between group assignment and these characteristics will be tested to explore potential moderators of treatment effect. We will repeat these analyses for the secondary outcomes (e.g., theoretical mediators)).

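### The adjusted, moderator and GLMM analyses do not restrict substance use, distress and process covariates to baseline, so values reported after WebApp access can enter the efficacy models

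*Combined protocol and SAP*

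**What the plan says.** - **Recall window (6.1.1, ATOD use).** Frequency of use is asked "over the past 30 days (3 months in 3-, 6-, 9-, and 12-month follow-up surveys". Section 7.3.3 gives the schedule: "Self-administered surveys will be done at baseline and months 1, 3, 6, 9, and 12". Baseline and month 1 are therefore on 30 days, and months 3, 6, 9 and 12 are on 3 months.
- **Adjustment list (10.1.1).** "The regression will be run with group assignment only in the model", and also with control for "socio-demographic characteristics, ATOD and psychological distress, and intervention-related process data (e.g., frequency of use, acceptability". Arm-by-characteristic interactions are then tested as possible moderators. No wave is named for any of these variables.
- **GLMM (10.3.1).** The general form writes its covariate term with subject and time subscripts ("Covariates_{ij" in the formula), whereas the arm term carries the subject subscript only. It does not name the covariates or refer back to the 10.1.1 list. The time points are described as "baseline and 4 follow-ups", although five follow-ups are scheduled.
- **Models without covariates (2.4).** The repeated-measures models for binary and continuous outcomes contain arm, time and their interaction only. The frequent-tester comparison is a two-sample Z-test of proportions.
- **Order of events (Study Abstract; 5.1).** Randomisation comes after consent and before the baseline survey. WebApp access comes after the baseline survey.

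**The concern.** A covariate in an efficacy model should be one that the intervention cannot have changed. Here the plan leaves that open. The 10.1.1 list cannot be read as baseline-only throughout, because frequency of use and acceptability exist only once the participant has used the WebApp. The GLMM notation separates a fixed arm term from time-indexed covariates. Intervention content is tailored partly to substance use (3.1), so an effect of GC on ATOD cannot be excluded.

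Three things are at stake:

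- If GC shifts ATOD or distress, adjusting for the current-wave value yields an arm effect without the part that acts through them. That is no longer the total effect of assignment.
- A moderator measured after exposure does not define subgroups that randomisation has balanced.
- Two analysts could follow the same text and fit different adjusted models, one with a pre-exposure 30-day covariate and one with a post-exposure covariate whose recall window changes at month 3.

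**Working it through.** The plan states no figure on this point, so the check is of the text, followed by illustrations under assumed inputs.

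**1. Which analyses can take a post-exposure covariate?**

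| Analysis | Covariates | Exposed? |
|---|---|---|
| 2.4 repeated-measures models | none | no |
| 2.4 frequent-tester Z-test | none | no |
| 10.1.1 arm-only regression | none | no |
| 10.1.1 adjusted regression | ATOD, distress and process data; wave not stated | yes |
| 10.1.1 moderator tests | same list | yes |
| 10.3.1 GLMM | unnamed, time-indexed | yes |

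**2. What conditioning on a wave-level value does.** Assume a linear model with direct arm effect d, covariate-outcome slope b and arm-induced shift s in the covariate. The total effect is d + b × s. The estimate adjusted for the wave-level covariate is d. The share lost is b × s / (d + b × s). With the assumed values d = 0.20 and b = 0.3:

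| s | Total effect | Wave-level adjusted | Share lost |
|---|---|---|---|
| 0 | 0.20 | 0.20 | 0% |
| 0.1 | 0.23 | 0.20 | 0.03/0.23 = 13% |
| 0.2 | 0.26 | 0.20 | 0.06/0.26 = 23% |
| 0.3 | 0.29 | 0.20 | 0.09/0.29 = 31% |

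A simulation of 400 trials (400 participants, 5 waves) agrees. For s = 0.1, 0.2 and 0.3, the unadjusted, wave-level adjusted and baseline-adjusted estimates were 0.228/0.199/0.228, 0.260/0.199/0.259 and 0.287/0.198/0.289.

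**3. Does the recall switch itself bias the arm effect?** A second simulation (300 trials of 480, linear outcome, categorical time) entered ATOD as a count, with the window lengthened from month 3.

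| Arm affects ATOD? | No ATOD term | Baseline ATOD | Wave-level ATOD |
|---|---|---|---|
| No | 0.301 | 0.301 | 0.300 |
| Yes (log rate lowered by 0.5) | 0.385 | 0.385 | 0.348 |

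With no arm effect on ATOD, the switch leaves the estimate unchanged. With one, the loss is (0.385 − 0.348)/0.385 = 10%, and baseline adjustment avoids it. A separate simulated check for spurious moderation gave error rates of 4% to 6%, so no inflation.

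**4. How different are the two windows?** Assume constant behaviour and take 3 months as 91.3 days. Counts of use days then grow by 91.3/30 = 3.04. If ATOD is coded as any use, with use occurring at a constant Poisson rate, a 30-day prevalence p becomes 1 − (1 − p)^(91.3/30): 10% becomes 27%, 20% becomes 49% and 30% becomes 66%. If rates vary between people (gamma-distributed, shape 0.3 to 1), 20% becomes 36% to 43% and 30% becomes 46% to 56%. The documents give neither the prevalence nor the coding, so these figures show only that the two windows measure different quantities.

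**The case against.** The strongest reply is that the plan never says current-wave ATOD will be entered. ATOD is described under the baseline-measures heading. Section 10.3.1 gives only a general form, a baseline covariate fits inside a time-indexed term, and the formula as it reads in the available text is imperfect, so one subscript is thin evidence. All of that stands. A reader might infer that ATOD is among the GLMM's time-indexed covariates, but 10.1.1 and 10.3.1 are not linked and the documents do not say so. What they do support is that wave-level values are not ruled out, and that one group on the 10.1.1 list, the process data, is post-exposure on any reading.

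Other stronger readings also fail:

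- **That the window change biases the treatment comparison.** The window is the same in both arms at every wave, and step 3 shows no bias from it alone. It follows the survey schedule, as the STI testing questions do.
- **That the main efficacy tests are compromised.** The section 2.4 analyses and the arm-only regression carry no covariates.
- **That the problem is measurement after randomisation.** The baseline survey itself follows randomisation. The line that matters is before or after WebApp access.
- **That re-tailoring would mistake the longer window for changed behaviour.** Section 5.4.1 says "the GC WebApp will be retailored after each follow-up survey", but on key questions that it does not name.

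It is also fair to say that tailoring to substance use is not the same as targeting it. No study hypothesis concerns substance use, and the reported pilot effects do not include it. Follow-up measurement of distress is not spelled out either; 5.4.1 says only that many baseline questions are repeated. These points bear on how likely a bias is. They do not settle which value the analyst should use.

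**Conclusion.** The concern holds as a gap in specification with a possible bias. It is confined to the adjusted, moderator and GLMM analyses. The plan as written admits covariates measured after WebApp access, and its process data can be nothing else.

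For ATOD and distress, the effect on the arm estimate is zero if GC does not move them. If it does, part of the total effect is removed. The losses of 13% to 31% and of about 10% rest on slopes, effects and shifts that were assumed, and they should not be quoted as estimates for this trial. The true size cannot be derived from the documents.

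The recall switch is a secondary matter of interpretation: a single coefficient, or a single definition of a user, would span a 30-day and a 3-month measure. How many waves fall on each side is itself unclear, because 10.3.1 counts four follow-ups and the schedule has five. The point does not reach the covariate-free analyses, but it should be settled before outcome data are seen.

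**What to change.** - **10.1.1 and 10.3.1:** state that adjustment covariates and moderators in efficacy models are values from the baseline survey, taken before WebApp access: 30-day ATOD and baseline distress. Write the GLMM term as `Covariates_i` and name its contents.
- **10.1.1:** leave intervention process data out of the adjusted efficacy model and its moderator tests. Engagement already has a place in the secondary analyses of 10.3.2.
- **Any time-varying ATOD analysis:** label it exploratory and define a measure standardised for the recall window, such as use per 30 days.

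The cost is SAP wording. The baseline values are already collected, and no survey needs to change. What is given up is adjustment for current-wave ATOD or distress in the efficacy models; such analyses remain available as exploratory.
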